6.1.2 Health, hospitalisation and referral outcomes

6.1.2.1 Proportion of children with a severe complication by Day 7

Severe complication is defined as death or secondary hospitalisation. Secondary hospitalisation refers to any delayed hospitalisation (occurring at any point greater than 24hrs after the Day 0 consultation) and any hospitalisation occurring without a referral. Information on death and hospitalisation will be taken from Day7 follow-up assessment.

Death will be counted in the numerator if death date is within 7 days of Day0 (7th day included). Hospitalisation will be counted in the numerator if the child was not referred at Day0 or hospital admission date is within 7 days of Day0 (7th day included) but after 24hrs of Day0.

The denominator will be all children recruited. Children for whom no death and hospitalisation data are available or withdrew prematurely from the study will be assumed to be alive and not hospitalised by Day7.

6.1.2.2 Proportion of children admitted to hospital within 24 hours of Day 0 consultation and as a result of a referral

Information on hospitalisation will be taken from Day7 follow-up assessment.

Hospitalisation will be counted in the numerator only if the child received a referral advice (as per definition above) at Day0 and hospital admission date is within the end of the following day. The denominator will be all children recruited.

Additionally, the proportion will be calculated and reported using only children who were referred as denominator.

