6.4 Outcomes

6.4.1 Quasi-experimental pre-post study

Two primary outcomes will be assessed between the pre-intervention and post- intervention period:

- ξ Proportion of children referred by a primary care healthcare provider to a higher level of care (either to a hospital or to an inpatient part of a larger primary healthcare facility) at Day 0 consultation
- ξ Proportion of children prescribed an antibiotic at Day 0 primary care consultation

These two outcomes are selected to reflect the intended impact on referral of children with severe disease (pulse oximetry and CDSA) and antimicrobial stewardship (CDSA). Severe complication outcomes are included in secondary outcomes rather than primary as, given the pre-post nature of the study, change in mortality / morbidity outcomes could be influenced by other events occurring between the baseline and post-intervention comparison phase.

Secondary outcomes:

- ξ Proportion of children with a severe complication (death or secondary hospitalisation) by Day 7
 - Secondary hospitalisation refers to any delayed hospitalisation (occurring at any point greater than 24 hours after Day 0 consultation) and any hospitalisation occurring without referral. The denominator is all enrolled children
- ξ Proportion of children admitted to hospital within 24 hours of the Day 0 primary care consultation and as a result of a referral
 - This is used as a proxy for 'appropriate referral' of children, as those with severe disease should generally be admitted to hospital. The denominator for this outcome is also all children enrolled in the study, rather than only referred children. This is because the proportion of referred children that are admitted may be high in routine care, in the context of an inappropriately low referral rate. The aim of the intervention is therefore to increase the overall referral rate of children with severe disease. Hospital admission is chosen as the proxy of severe disease rather than using primary care classification of severe disease, as there are inadequacies in the classification of severe disease in routine practice
- ξ Proportion of children who completed referral as reported at day 7 follow-up
- ξ Proportion of children cured (defined as caregiver reported recovery from illness) at Day 7 follow-up

Sub-groups for analysis of primary and secondary outcomes:

- ξ Age (under 2 months, 2 – 12 months, 13 – 59 months)
- ξ Sex
- ξ Presentation with cough / difficulty breathing

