6.1.1 General definitions

Day 7 assessment

Day 7 assessment refers to information reported by the caregiver after Day 0 and recorded in Day 7 form. Data collected as part of unscheduled visits are also integrated in these forms. If multiple successful follow-up assessments for the same child are recorded within the Day7 database, the most recent follow-up assessment will be used. To limit potential recall bias, assessments conducted far beyond the expected follow-up time will be dropped, i.e. 30 days from Day 0.

Death

A child will be considered deceased if, from Day 7 assessment, his/her status at the time of follow-up is “deceased”. In case of implausible death date (i.e. prior to enrolment date), death will be assumed to be within 7 days of Day0.

Hospitalisation

A child will be considered hospitalised if, from Day 7 assessment, he/she went to a hospital, was admitted overnight or if his/her status at the time of follow-up is “hospitalised”. In case of implausible hospitalisation date (i.e. prior to enrolment date), hospitalisation will be assumed to be within 7 days but after 24hrs of Day0.

Hospitalisation within 24hrs of Day0

For the purpose of primary analysis, a child will be considered admitted to hospital within 24hrs of Day0 consultation if the date of hospitalisation is the same as Day0 date or is one day after Day0 date.

Referral

A child will be considered to be referred (either to a hospital or to an inpatient part of a larger primary healthcare facility) if, at Day0, the research assistant confirms that an urgent referral advice was recorded for the child. If urgency is unknown, referral will be assumed to be urgent.

Antibiotics

Antibiotics will be defined in accordance with the WHO antibiotic point prevalence survey (PPS) methodology [4, 5, 6] and therefore only antibacterials for systemic use will be taken into account.

SpO2 values

SpO₂ should be recorded during the Day0. For the outcomes, the following measures will be taken for spurious and missing SpO₂ values:

- If SpO₂ value is not available, the child will be assumed normoxaemic
- If $70 \leq \text{SpO}_2 < 90\%$, the child will be assumed (with accuracy) to have severe hypoxaemia
- If $40 \leq \text{SpO}_2 < 70\%$, the child will be assumed (with low accuracy) to have severe hypoxaemia
- If $\text{SpO}_2 < 40\%$, the value will be considered spurious (e.g. due to incorrect dataentry) and treated as not available, i.e. the child will be assumed normoxaemic.

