6.2.4 Pre-planned Sensitivity Analyses

Sensitivity analyses on the primary outcomes are planned and will be conducted:

- ξ On first encounters, which will include only the first enrolment episode of each child during the study period (as some children may attend the facility on more than one occasion). Separate presentations are identifiable from Day0 form as the caregiver is asked whether the child attended previously and within 28 days. This is the minimum number of days required for the disease episode to be considered a new one and not a repeat visit.
- ξ Looking at different referral definitions¹:
 - ο A child will be considered to be referred if, at Day0, the caregiver confirms that the child was urgently referred or the research assistant confirms that an urgent referral advice was recorded for the child. If urgency is unknown from both sources, referral will be assumed to be urgent.

¹ Urgency, as reported by the caregiver, was introduced only in the post-intervention period in Kenya. For the pre-intervention period, urgent referrals will be defined based on the registry alone, as described for the primary analysis.

- A child will be considered to be referred if, at Day0, caregiver confirms that the child was urgently referred *and* the research assistant confirms that an urgent referral advice was recorded for the child.

Additionally, a set of sensitivity analyses shall be carried out based on different definitions of pre and post-intervention periods:

- ξ Pre-intervention and post-intervention defined based on periods of the year that match in the pre and post intervention.
- ξ Pre-intervention defined as primary analysis and post-intervention from country-specific relevant dates (i.e. formal initiation after the strike in Senegal and intensive supervision in Kenya) to the end of data collection.

Sensitivity analyses on the secondary outcomes related to hospitalisation will be conducted looking at different hospitalisation appropriateness (based on different definitions of primary and secondary hospitalisations). Same day (Day0), 3 days and 7 days from Day0 will be used as cut-offs for different primary and secondary hospitalisation definitions.

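### Severe complication counts a Day 0–1 admission only when no referral was recorded, so a change in recorded referral alone can lower it, and no referral-independent comparison is planned

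*SAP*

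**What the plan says.** SAP 6.1.2.1: "Severe complication is defined as death or secondary hospitalisation". Secondary hospitalisation has two routes, admission more than 24 hours after the Day 0 consultation and "any hospitalisation occurring without a referral". The numerator rule reads "Hospitalisation will be counted in the numerator if the child was not referred at Day0 or hospital admission date is within 7 days of Day0", with the second route then limited to admissions after 24 hours. Protocol 6.4.1 has the same two routes, the second worded as "any hospitalisation occurring without referral. The denominator is all enrolled children".

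SAP 6.1.1 supplies the two switches. An admission is within 24 hours if "the date of hospitalisation is the same as Day0 date or is one day after Day0 date". A child is referred if "the research assistant confirms that an urgent referral advice was recorded for the child", and unknown urgency is taken as urgent. This referral variable is also the first primary outcome (SAP 6.1.2.4).

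SAP 6.1.2.2 counts referred children admitted by the end of the day after Day 0. Its denominator, like that of 6.1.2.1, is all recruited children. Protocol 6.4.1 gives the reason for that outcome: "The aim of the intervention is therefore to increase the overall referral rate of children with severe disease".

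For the hospitalisation outcomes, SAP 6.2.4 plans sensitivity analyses in which "Same day (Day0), 3 days and 7 days from Day0 will be used as cut-offs". The alternative referral definitions in that section are for the primary outcomes only.

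**The concern.** One of the two conditions that define the outcome is a variable that the intervention is meant to change. Take a child admitted on Day 1. If the provider recorded no referral, the child has a severe complication. If the provider recorded an urgent referral, the child does not, and counts under 6.1.2.2 instead. The admission is the same in both cases. Because referral is defined by what was recorded, fuller documentation could also shift the count.

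SAP 3.5 sets out the hypothesis that adverse health outcomes will fall, and severe complication is the first-listed secondary outcome bearing on it. A fall could be read as fewer severe complications when part of it is reclassification. Protocol 7.3.4 also draws on mortality and secondary hospitalisation to model effectiveness, so the reclassification could carry into cost per DALY averted.

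**Working it through.** **1. The plan's own figures.** The documents give no rate, effect size or power for severe complication, and no admission rate. The only sample size is for referral. Inputs (SAP 3.4, protocol 6.6.1): 3% to 4.5%, 80% power, alpha 0.05 (two-sided assumed), ICC 0.005. Without clustering this needs 2,518 children per period.
- Kenya: design effect 1 + (690 − 1) × 0.005 = 4.445; 2,518 × 4.445 = 11,193; ÷ 690 = 16.2, so 17 facilities and 11,730 children.
- Senegal: 1 + (510 − 1) × 0.005 = 3.545; 2,518 × 3.545 = 8,926; ÷ 510 = 17.5, so 18 facilities and 9,180 children.

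Both stated figures are reproduced. They serve below only as denominators.

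**2. The rule applied to every admission by Day 7.**

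| Admission date | Urgent referral recorded | None recorded |
|---|---|---|
| Day 0 or Day 1 | 6.1.2.2 | 6.1.2.1 |
| Day 2 to Day 7 | 6.1.2.1 | 6.1.2.1 |

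Only the first row depends on referral. There is one small exception: SAP 6.1.1 places an admission with an implausible date after 24 hours, so it counts in 6.1.2.1 even for a referred child.

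**3. Size of pure relabelling (all inputs assumed).** Let u be the proportion of children with an unreferred Day 0–1 admission, d the proportion with any other severe complication, and f the share of the u group who become referred. Deaths and admissions are held fixed.
- Pre = u + d; post = u(1 − f) + d; fall = u × f.
- Ranges: u 0.25–1.0%, d 0.5–1.0%, f 20–60%.
- Smallest: u = 0.25%, d = 1.0%, f = 20%: 1.25% to 1.20%, RR 0.96.
- Middle: u = 0.5%, d = 1.0%, f = 40%: 1.50% to 1.30%, OR 0.86; 176 to 152 events per 11,730.
- Largest: u = 1.0%, d = 0.5%, f = 60%: 1.50% to 0.90%, RR 0.60; 176 to 106 events per 11,730.

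In Kenya the chance of p < 0.05 from relabelling alone is about 4–5% in the smallest case. In the largest it is about 99% ignoring clustering and 52% with design effect 4.445, which borrows the referral ICC.

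**4. The planned cut-offs.** Assumed cohort per 10,000 children, 200 admissions in total. Unreferred: 30 on Day 0, 20 on Day 1, 20 on Days 2–3, 20 on Days 4–7 (90). Referred: 60, 30, 10, 10 (110). Then 40% of unreferred admitted children become referred and nothing else changes. Secondary hospitalisation is all unreferred admissions plus referred admissions after the cut-off.

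| Cut-off | Before | After | RR |
|---|---|---|---|
| Same day | 90 + 50 = 140 | 54 + 74 = 128 | 0.91 |
| Planned (Day 0–1) | 90 + 20 = 110 | 54 + 36 = 90 | 0.82 |
| 3 days | 90 + 10 = 100 | 54 + 18 = 72 | 0.72 |
| 7 days | 90 + 0 = 90 | 54 + 0 = 54 | 0.60 |
| Any hospitalisation | 200 | 200 | 1.00 |

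The same-day version shrinks the shift without removing it, and the later versions enlarge it. At 7 days secondary hospitalisation is simply unreferred admission. Under the planned cut-off, 6.1.2.2 moves from 60 + 30 = 90 to 72 + 38 = 110, the mirror of the fall in 6.1.2.1.

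**5. The opposing movement.** Start from the middle case (1.50% to 1.30%). Suppose referral rises by 1.5 points and a share g of the newly referred have an added admission after 24 hours. Post = 1.30% + 1.5% × g: 1.45% at g = 10% and 1.60% at g = 20%. The outcome can therefore rise.

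**The case against.** The definition is deliberate and disclosed. An unreferred child who is soon admitted is plausibly a missed case, and moving that child to referred-and-admitted is what the plan treats as appropriate referral. Calling the move no health change is itself an assumption. The outcome is also secondary: protocol 6.4.1 keeps it out of the primary set because of other influences over time, protocol Tab. 8 calls the outcome assessment exploratory, and SAP 6.2.1 models secondary outcomes only if numbers allow. All of this stands, and it is why the outcome should be kept.

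A reader might infer that relabelling could not be told from benefit. The documents do not support that. Outcome 6.1.2.2 has the same denominator and is summarised by period, and the hospitalisations counted in 6.1.2.1 and 6.1.2.2 do not overlap. Pure relabelling would show as a fall in one and a rise in the other.

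The safeguard is partial. Adding the two outcomes does not give death or any hospitalisation, because a referred child admitted early who then dies counts in both, and no estimate or interval is planned for the sum. The harms summary (SAP 6.5 with 4.3) gives deaths and secondary hospitalisations separately, but overall and by use of intervention, not by period, and it does not separate unreferred from delayed admission. The denominator for length of stay (SAP 6.1.2.3) is all hospitalised children, but it is not combined with death or specified as a comparison.

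**Conclusion.** The point holds as a limit on interpreting one secondary outcome. The primary outcomes are unaffected. A change in recorded referral alone can lower severe complication, and no planned analysis estimates the effect independently of referral. Under assumed inputs the relabelling part is a fall of 0.05 to 0.60 percentage points (RR 0.96 to 0.60). These values illustrate the mechanism and do not predict the result. If few unreferred children are admitted by Day 1, the shift may be too small to detect.

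Three stronger readings are tempting but not supported:
- That the intervention aims to raise referral by 50%. That figure is the minimum detectable difference in the sample size; the stated aim has a direction and no number.
- That the outcome will fall. Step 5 shows that later admissions among newly referred children can offset or reverse the relabelling.
- That the SAP states that the referral condition is kept in the sensitivity analyses. It speaks of different definitions and lists only time cut-offs. Keeping the condition is the natural reading, not an explicit statement.

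**What to change.** Keep 6.1.2.1 as defined, and add to the SAP:
- By period, its components: death; admission after 24 hours whatever the referral status; unreferred admission within 24 hours. State that a child can appear in more than one row. State also whether the Day 7 limit applies to unreferred admissions, since the numerator sentence, read literally, attaches it only to the delayed ones.
- One sensitivity model, fitted as for the other binary outcomes: death or any hospitalisation by Day 7, regardless of referral.
- A sentence saying that 6.1.2.1 will be interpreted together with 6.1.2.2.

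This is a cheap improvement: a few table rows and one model, from Day 0 referral, admission date and vital status, all of which are already collected. If analysis has begun, SAP 1.1 permits additional analyses that are identified and justified. The downside is that any hospitalisation can rise through appropriate referral, so the new estimate must be read beside the components and should not replace the defined outcome.

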Additionally, visit information from government-designated hospital records will be collected retrospectively for children whose caregiver reported at Day 7 phone follow-up that they attended hospital, including clinical assessment on arrival (vital signs, admitting diagnosis), admission details (duration, if oxygen was administered, intensive care admission) and admission outcome (final diagnosis, discharge against medical advice, death). The same data will be collected for children who attended a non-hospital higher-level of care (emergency or admission unit of a primary or secondary care facility).

It is expected that some participants may present at the same or another health facility enrolled in the study during the follow-up period. These visits and the findings will be recorded on the appropriate scheduled / unscheduled visit eCRFs.

[figure not shown]
[figure not shown]
[figure not shown]

Fig. 5. Flowchart of the pre-post study. CDSA = Clinical Decision Support Algorithm. CG = Caregiver. HCP = Healthcare provider. OPD = Out-patient department.

Tab. 4. Schedule of the visits and associated CRFs for the pre-post study. The different types of staff collecting data are represented by the following icons:

Research assistant rotating
between different referral health
facilities

Call centre-based research assistant

		Health facility baseline visit		Higher level of care visit ^{1,2}		Follow-up or unscheduled visit at enrolled health facility		Phone follow-up
		Time point		Day 0		Day 0-7		Day 7 [7 - 10]
		Data collection method		Prospective data collection		Review of medical records		Phone interviews
		Study phase		Pre	Post ³			Pre
Events		Forms						Post ³
Informed consent				-				
Screening				TIMCI-01				
Identification & contact information	Full identification	TIMCI-02a						
	Contact information	TIMCI-02b						
	Identification and contact information check	TIMCI-02c						
	Referral facility identification	TIMCI-02d						
	Follow-up identification check	TIMCI-02e						
Socio-demographics		TIMCI-03						
Visit info	Care seeking behaviour, transport and costs for visiting health facility reported by caregiver	TIMCI-04a						
	Visit and admission info recorded by referral facility (medical records, registries) ²	TIMCI-04b						
	Patient journey reported by caregiver at follow-up	TIMCI-04c						
Clinical presentation & medical history	Clinical presentation and medical history reported by caregiver at baseline	TIMCI-05a						

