Data that will be collected at Day 7 follow-up will include cure status (recovery from illness as reported by the caregiver), hospitalisation and death between Day 0 and Day 7. If appropriate, name of the referral facility and duration of hospitalization will be collected to facilitate the retrospective data collection at referral hospital level.

Higher level of care visit

Data collection at this level of care will be conducted retrospectively. A quantitative research assistant using the EDC mobile application will collect data from referral facility records, registries and discharge summaries for children whose caregiver reported at Day 7 phone follow-up that they attended a government-designated referral facility between Day 0 and Day 7. This includes attendance to hospital or emergency / inpatient area of a larger primary or secondary care facility (e.g., study facilities that can admit paediatric patients). Personally identifiable information will be collected to cross-check the identity of the patients. Arrival date and time, basic clinical information on arrival and, if admitted, admission and discharge diagnosis and admission duration will be collected. If available, data on oxygen saturation at admission, oxygen administration and intensive care unit (ICU) admission and duration will also be recorded.

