7.2.4 Data quality assurance and control

Quality assurance activities across all studies will be more intense during study start-up to ensure quality data practices are instituted from the start of the trial. Further details will be given in the DMP and SOPs.

All research assistants will be trained to provide information and seek written consent using the information and consent form. Separate trainings will cover all aspects of quantitative data collection and all aspects of qualitative data collection. A competency assessment using scenarios will be done before commencing field work.

Data reconciliation between the different visits of the same child will be one of the most crucial data quality activities in the pre-post study. Specific procedures will be developed for this purpose. To identify repeat visits of children that may re-attend the study facility where they enrolled, or any other study facility during the follow-up period, participants will be given a study card (or sticker) with a unique ID number. Retrospective search for data at referral level will be restricted to facilities within the geographical area where the study is running and will be targeted to include only children reported to have attended hospital by the caregiver at follow-up and those lost to follow-up. The name of the referral facility will be requested during the follow-up call. If available, it should further restrict the scope of the search and the probability of negative matches when cross-checking the participant identity. Children who re-attend any study facility more than 28 days after their previous enrolment will be enrolled for the new disease episode and given a new ID number. If available, the old ID number will be recorded to facilitate linking of the different disease episodes. Data to be potentially reconciled will be flagged by automated cross-check of a set of personal identifiers. Given that personal identifiers may not be identically recorded at each visit, fuzzy matching methods will be used to calculate a score of similarity between records and likelihood that they relate to the same child. Reconciliation of records with high similarity scores will be manually validated.

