6.3 Missing Data

Missing values will be primarily due to children lost to follow-up and not reached at Day 7.

Primary outcomes are based on information collected at Day0 through a structured data collection process that prevents missing values due to compulsory data entry. Therefore, missing data on the primary outcomes are not anticipated.

Analysis on secondary outcomes that rely on Day 7 follow-up data will be performed assuming the best case scenario (alive and not hospitalised) for children lost to follow-up or withdrawn.

Additionally, missing data will be described by pre and post intervention period and by relevant indicators, such as referral and severe disease to visually inspect for imbalances.

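### Death and hospitalisation are counted only from the caregiver's Day 7 report, lost children are scored event-free, and the protocol contradicts itself on whether hospital records are searched for them

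*SAP*

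**What the plan says.** **Source of events.** SAP 6.1.1 explains that "Day 7 assessment refers to information reported by the caregiver after Day 0 and recorded in Day 7 form"; data from unscheduled visits are folded into the same form, and referral-facility records are not mentioned. Death is read from that assessment. So is admission: "A child will be considered hospitalised if, from Day 7 assessment, he/she went to a hospital", was kept overnight, or was in hospital at the time of the call. SAP 6.1.2.1 (severe complication) repeats the rule: "Information on death and hospitalisation will be taken from Day7 follow-up assessment". SAP 6.1.2.2 (admission within 24 hours on referral) uses the same source for hospitalisation.

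**Children without Day 7 data.** Both outcomes use all recruited children as the denominator. SAP 6.1.2.1 scores children with no death or hospitalisation data, and those who withdrew, as free of events. SAP 6.3 analyses the Day 7 outcomes "assuming the best case scenario (alive and not hospitalised) for children lost to follow-up or withdrawn", and states no exception. In the same spirit, SAP 6.1.2.5 scores children without Day 7 data as not having attended hospital, and SAP 6.1.2.7 scores them as cured.

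**Record search.** Protocol 7.2.4 targets the retrospective referral-level search to "include only children reported to have attended hospital by the caregiver at follow-up and those lost to follow-up". Protocol 6.5.1 is narrower: "visit information from government-designated hospital records will be collected retrospectively for children whose caregiver reported at Day 7 phone follow-up that they attended hospital". Protocol 7.1.1 has the same limit, and the referral log in Protocol 7.2.2 is generated from the Day 7 phone results. The records hold what is needed: "Arrival date and time, basic clinical information on arrival and, if admitted, admission and discharge diagnosis and admission duration will be collected", and Protocol 6.5.1 lists death among the admission outcomes.

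**Implausible dates.** SAP 6.1.1: "In case of implausible hospitalisation date (i.e. prior to enrolment date), hospitalisation will be assumed to be within 7 days but after 24hrs of Day0".

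**The concern.** Deaths and secondary hospitalisations form one of the important secondary outcomes in the protocol summary. They are also how SAP 6.5 evaluates safety, and Protocol 7.3.4 feeds severe outcomes into the cost-effectiveness model. A family that cannot be reached may be one whose child was admitted or died, so these are the children for whom an event-free default is least safe. In a pre-post comparison the default also converts a difference in follow-up between periods into a difference in event rates. The protocol appears to have planned a partial remedy in its record search, but its sections disagree on whether that search covers lost children, and the SAP does not use it for these outcomes.

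**Working it through.** **1. The two readings of the protocol.**
- If Protocol 7.2.4 is followed, records are searched for lost children and some admissions or deaths may be found. The SAP definitions read only the Day 7 assessment, and SAP 6.3 sets every lost child to event-free. Such events have no stated route into the numerator.
- If Protocol 6.5.1, 7.1.1 and the log in 7.2.2 are followed, lost children are not searched for, and only the default remains.

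The analysed value is event-free in both cases.

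**2. Inputs.** The plan states no figure for severe complication, so there is none to reproduce. From the documents I take only the planned Kenyan period size, 17 × 690 = 11,730 (Protocol 6.6.1), as a scale. Assumed, because the documents give no values: loss L from 2% to 10%; risk in lost children RR = 1 to 3 times that in reached children; records find a share f = 0.25 to 0.5 of lost children's events.

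**3. Share of events counted.** With event rate p in reached children:
- counted rate = (1 − L)p
- full rate = (1 − L)p + L·p·RR
- share counted = (1 − L) / [(1 − L) + L·RR]

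At L = 2%, RR = 1 the share is 0.98 / 1.00 = 98%. At L = 10%, RR = 3 it is 0.90 / 1.20 = 75%.

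Per 11,730 children with p = 1%:
- L = 5%, RR = 1: 11,730 × 0.05 × 0.01 = 5.9 events scored as non-events; records would recover 1.5 to 2.9.
- L = 10%, RR = 3: 11,730 × 0.10 × 0.03 = 35.2 scored as non-events; records would recover 8.8 to 17.6.

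**4. Bias in the pre-post comparison.** Set the overall event rate to 1% in both periods, so there is no true effect. The rate in reached children is then 1% / [(1 − L) + L·RR], and the counted rate is (1 − L) times that.

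| Loss pre / post | RR | Counted pre | Counted post | Apparent OR |
|---|---|---|---|---|
| 5% / 5% | 1 or 3 | equal | equal | 1.00 |
| 5% / 10% | 1 | 0.950% | 0.900% | 0.95 |
| 5% / 10% | 3 | 0.864% | 0.750% | 0.87 |
| 10% / 5% | 1 | 0.900% | 0.950% | 1.06 |
| 10% / 5% | 3 | 0.750% | 0.864% | 1.15 |

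**5. What a remedy would buy in the third row.** Events in lost children are 1.000 − 0.864 = 0.136% pre and 1.000 − 0.750 = 0.250% post.
- f = 0.25: 0.898% v 0.813%, OR 0.90.
- f = 0.5: 0.932% v 0.875%, OR 0.94.
- Known Day 7 status only: 0.864 / 0.95 = 0.909% v 0.750 / 0.90 = 0.833%, OR 0.92.

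Each moves the estimate towards 1 and none removes the bias. With RR = 1, the known-status rates are 1% in both periods and unbiased.

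**6. The date default.** Take a referred child admitted on Day 0 whose admission date is entered as before enrolment. SAP 6.1.1 places the admission after 24 hours. By SAP 6.1.2.1 the child becomes a severe complication, and by SAP 6.1.2.2 the child leaves the 24-hour numerator.

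**The case against.** **What stands.** The wording in SAP 6.1.2.1 about having no death and hospitalisation data could, read alone, spare a child with a hospital record. The source sentence beside it and the unconditional rule in SAP 6.3 point the other way, so at best the SAP is ambiguous. SAP 5.4 and 6.3 show follow-up and missing data by period, so unequal loss would be seen; nothing planned corrects for it. Repeat calls, community contacts and the inclusion of unscheduled visits keep the lost group smaller than the number who miss the first call. A single uniform source is defensible, since caregivers can report private admissions and the records searched are those of government-designated facilities.

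On dates, entry checks (Protocol 7.2.2) should catch some errors. In the 7-day cut-off analysis of SAP 6.2.4, the defaulted child should count as a primary hospitalisation. That analysis also reclassifies genuine late admissions, so it tests the default only in part, and the main analysis is unchanged.

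**Stronger readings that the documents do not support.**
- A reader might infer that the search will find deaths which the SAP then discards. That holds only if Protocol 7.2.4 prevails over 6.5.1, 7.1.1 and the 7.2.2 log.
- A reader might infer that harm would be hidden or an effect reversed. One can construct this: with 10,000 children per period, 5% then 15% loss, and risks of 1% in reached and 2% in lost children, 95 v 85 events are counted against a full 105 v 115. The loss figures are invented, the case builds in a true worsening, and the bias can run either way.
- A reader might treat this as the most important secondary outcome. No passage ranks it so; Protocol 6.4.1 gives reasons for keeping it out of the primary outcomes, and Tab. 8 calls the outcome assessment exploratory.

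**Conclusion.** The point holds as a gap in outcome definition and an unresolved contradiction in the protocol. Whichever protocol text is followed, events in lost children are scored as non-events, and no planned sensitivity analysis changes the source or the missing-data rule. Over the assumed ranges the plan would count 98% down to 75% of events. With a twofold difference in loss between periods (5% and 10%) and no true effect, the apparent odds ratio lies between 0.87 and 1.15, depending on which period loses more and on the risk in lost children. With equal loss and equal relative risk, the comparison is not biased in these scenarios, although the counts are still low. The true size cannot be derived from the documents. The date default is a smaller, separate misclassification. Both issues concern secondary outcomes and the harms summary; referral and antibiotic prescription are recorded at Day 0 and are untouched. The change should be made before analysis, but it does not threaten the primary result.

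**What to change.** 1. Reconcile Protocol 6.5.1, 7.1.1 and the 7.2.2 log with 7.2.4, so that the record search covers lost children in the same way in both periods. If the baseline search did not cover them and can no longer be done, say so, and use record events only in a sensitivity analysis.
2. In SAP 6.1.1, 6.1.2.1, 6.1.2.2, 6.3 and 6.5, count a death or hospitalisation recorded on the Day 7 form or in a matched referral-facility record (forms TIMCI-04b and 09c). Apply the event-free default only to children with neither source. Report events by source and period.
3. Carry the rule into SAP 6.1.2.5 and 6.1.2.7. Otherwise a child found dead in records would also be scored as cured, and one found admitted on referral would be scored as not having attended hospital.
4. Where the caregiver's admission date precedes enrolment, use the date in the matched facility record; use the present default only if there is none. Report how many dates were handled each way, by period.
5. Repeat the severe-complication, 24-hour admission and harms rates among children with known Day 7 status, by period.

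**Cost.** SAP wording, a small protocol clarification and real matching work: Protocol 7.2.4 foresees fuzzy matching with manual validation, and it relies on the follow-up call for the facility name, which lost children will often lack. Recovery is partial, because private facilities, deaths outside hospital and facilities outside the study area are missed. Item 5 is therefore needed even if items 1 to 4 are done.
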